## 1.0 Background

### 1.1 Neoadjuvant therapy for hormone receptor positive breast cancer

Endocrine therapy is the cornerstone of treatment for patients with hormone-receptor (HR)-positive breast cancer. The presence of hormone receptors, especially estrogen receptor (ER), is a clear positive predictor of efficacy of adjuvant hormone therapy (HT) [1] [2]. Chemotherapy is less effective in the genetically and immunohistochemically defined (ER+/HER2-) luminal subtype when compared with the HER2-enriched and basal-like subtypes[3, 4]. Oncotype DX, developed by Genomic Health, is a diagnostic test that quantifies the likelihood of disease recurrence in women with early-stage hormone receptor positive breast cancer and assesses the likely benefit from certain types of chemotherapy. A prospective analysis of archived tissue from 367 postmenopausal, hormone receptor-positive, node-positive patients with invasive breast cancer treated on Southwest Oncology Group (SWOG) 8814 with tamoxifen or tamoxifen plus chemotherapy, suggests that only the subset of patients with intrinsically more biologically aggressive cancers, as defined by a high Oncotype Dx Recurrence Score (RS), appears to benefit from the addition of chemotherapy, whereas patients with low-intermediate RS may not have a significant benefit from chemotherapy. Further analysis incorporating determination of recurrence score by RT-PCR showed that after adjusting for number of lymph nodes involved, patients with high recurrence score had worse outcomes [5]. Patients treated with chemotherapy followed by tamoxifen had a 10-year disease free survival (DFS) of 55% and a 10-year overall survival (OS) of 68% [6]. An ongoing large randomized phase III clinical trial (SWOG 1007) is designed to evaluate the benefit from chemotherapy for ER positive breast cancer with 1-3 positive lymph nodes and an Oncotype Dx recurrence score of < 25 (low-intermediate recurrence scores).

In recent years, neoadjuvant therapy has been increasingly offered to breast cancer patients to facilitate tumor down-staging and to better understand tumor response to therapy [7]. Although neoadjuvant endocrine therapy has not been studied as extensively as neoadjuvant chemotherapy, neoadjuvant hormonal therapy is, in general, considered to be a suitable option for hormone receptor (HR)-positive patients who are unfit for chemotherapy or surgery with mild toxicity profile [8-10]. In the European Cooperative Trial in Operable Breast Cancer, pathologic complete response (pCR) after neoadjuvant chemotherapy was observed in 42% of patients with ER-negative tumors, compared with 12% in the ER-positive group [11-13]. In four phase III trials, differences in neoadjuvant treatment outcomes between aromatase inhibitors (AIs) and tamoxifen were studied. Clinical response rates ranged from 38% to 70% for AIs and from 36% to 51% for tamoxifen. Overall AIs have demonstrated superior results when compared with tamoxifen in postmenopausal patients [14-17].

More recently, attempts have been made to quantitate response to neoadjuvant endocrine therapy. Post-treatment Ki67 can be of prognostic value, as shown by Ellis et al., who developed a preoperative endocrine prognostic index (PEPI) score for the prediction of recurrence free survival (RFS). The PEPI score incorporates post-treatment pathological

tumor size, pathological node status, level of ER expression and the proliferative rate (defined by the percent of cells expressing Ki67) [8].

## **1.2 PI3kinase/AKT/mTOR signaling pathway in hormone receptor positive breast tumors.**

The phosphatidylinositol 3-kinase (PI3K)/AKT/mTOR signaling pathway plays an important role in cell survival, proliferation, angiogenesis and metabolism [18, 19]. mTOR, a serine/threonine protein kinase that belongs to the PI3kinase protein family, is frequently activated during carcinogenesis via genetic and epigenetic alterations. Abnormalities of the PI3kinase/AKT/mTOR signaling pathway are some of the most common molecular anomalies in breast cancer, and many of these abnormalities are detected in HR-positive tumors [1]. Activation of mTOR pathway leads to PI3K gene activation, phosphatase and tensin homolog (PTEN) loss and high levels of AKT expression in 16-48% of breast cancer patients [20-22]. A substrate of mTOR complex 1 (mTORC1), called S6 kinase 1, phosphorylates the activation function domain 1 of the ER, which is responsible for ligand-independent receptor activation[23, 24]. High levels of phosphorylated mTOR were correlated with nodal metastasis and poor prognosis in breast cancer patients [25]. Preclinical studies have shown that upregulation of the PI3K-mTOR pathway is a mechanism of resistance to endocrine therapy, and sensitivity to endocrine therapy can be restored by treatment with everolimus or other mTOR inhibitors [26, 27]. Interestingly, the rate of PI3K mutations is highest in low/intermediate grade and Luminal A breast cancers [28, 29]. This tumor subset is also thought to be less likely to benefit from chemotherapy.

Everolimus (Afinitor, Novartis) is an oral sirolimus (formerly called rapamycin) derivative that inhibits its mTOR through allosteric binding to mTORC1 potently [23, 30]. Everolimus has been recently approved for use in patients with advanced breast cancer progressing on a nonsteroidal aromatase inhibitors in combination with the steroidal aromatase inhibitor exemestane based on the results of BOLERO-2 which showed a PFS benefit in favor of the exemestane and everolimus combination arm compared to exemestane alone[31]. The BOLERO-2 study randomized 724 patients with metastatic hormone receptor positive breast cancer who had progressed on prior estrogen-deprivation therapy to receive exemestane or exemestane in combination with everolimus. The initial analysis, based on investigator assessment, demonstrated a significant improvement in progression-free survival (hazard ratio 0.43; 95% CI 0.35-0.54). On central review, the median time to progression was 4.1 months in the exemestane arm and 10.6 months in the combination arm. In addition, response rate and clinical benefit rate were both significantly superior with the combination, and while there was some increase in toxicity, there was no difference in quality of life during treatment in the two arms of the study [32]. The most common Grade 3 or 4 adverse events were stomatitis, anemia, hyperglycemia, fatigue and pneumonitis. Therefore, the combination of endocrine therapy and everolimus resulted in an increased antitumor effect in groups of patients without prior therapy, limited prior therapy and even extensive prior endocrine treatment suggesting that targeting mTOR activation may be implicated in restoring endocrine resistance.

## 1.3 Everolimus

Everolimus is a novel derivative of rapamycin. It has been in clinical development since 1996 as an immunosuppressant in solid organ transplantation. Everolimus is approved in Europe and other global markets (trade name: Certican®) for cardiac and renal transplantation, and in the United States (trade name: Zortress®) for the prevention of organ rejection of kidney transplantation. Afinitor® was approved for adults with advanced renal cell carcinoma (RCC) after failure of treatment with sunitinib or sorafenib in 2009. In 2010, Afinitor® received United States (US) approval for patients with subependymal giant cell astrocytoma (SEGA) associated with tuberous sclerosis complex (TSC). Everolimus is also available as Votubia® in the European Union (EU) for patients with SEGA associated with TSC who require therapeutic intervention but are not candidates for curative surgical resection. Afinitor® was approved for “progressive pancreatic neuroendocrine tumor (PNET) in patients with unresectable, locally advanced, or metastatic disease” in 2011 in various countries, including the US and Europe. In 2012 Afinitor® received approval for the treatment of postmenopausal women with advanced hormone receptor-positive, HER2-negative breast cancer (advanced HR+ BC) in combination with exemestane, after failure of treatment with letrozole or anastrozole. Furthermore in 2012, Afinitor® received approval for the treatment of patients with TSC who have renal angiomyolipoma not requiring immediate surgery. In the US, Afinitor® was approved in 2016 for advanced non-functional NET of gastrointestinal (GI) or lung origin.

Approximately 44,060 cancer patients (excluding those patients who received marketed Afinitor®, those on planned and roll over studies as well as excluding investigator-sponsored studies) have been treated with everolimus as of 31-Mar-2016

- 25,356 patients in Novartis-sponsored clinical trials
- 2,043 patients in the individual patient supply program

### 1.3.1 Everolimus mechanism of action

Everolimus is a derivative of rapamycin which acts as a signal transduction inhibitor ([Table 1](#), [Figure 1](#)). Everolimus selectively inhibits mTOR (mammalian target of rapamycin), specifically targeting the mTOR-raptor signal transduction complex. mTOR is a key serine-threonine kinase in the PI3K/AKT signaling cascade, which is known to be dysregulated in a wide spectrum of human cancers [33].

Everolimus is being investigated as an anticancer agent based on its potential to act

[figure not shown]
- directly on the tumor cells by inhibiting tumor cell growth and proliferation;

- indirectly by inhibiting angiogenesis leading to reduced tumor vascularity (via potent inhibition of tumor cell VEGF (vascular endothelial growth factor) production and VEGF-induced proliferation of endothelial cells).

**Table 1** **Everolimus - Drug substance**

Chemical name	(1R,9S,12S,15R,16E,18R,19R,21R,23S,24E,26E,28E,30S,32S,35R)-1,18-dihydroxy-12-{(1R)-2-[(1S,3R,4R)-4-(2-hydroxyethoxy)-3-methoxycyclohexyl]-1-methylethyl}-19,30-dimethoxy-15,17,21,23,29,35-hexamethyl-11,36-dioxa-4-aza-tricyclo[30.3.1.0  ]hexatriaconta-16,24, 26,28-tetraene-2,3,10,14,20-pentaone
International non-proprietary name	Everolimus

**Figure 1** **Chemical structure of Everolimus**

At the cellular and molecular level, Everolimus acts as a signal transduction inhibitor. It selectively inhibits mTOR (mammalian target of rapamycin), a key protein kinase which regulates cell growth, proliferation and survival. The mTOR kinase is mainly activated via the phosphatidylinositol 3-kinase (PI3-Kinase) pathway through AKT/PKB and the tuberous sclerosis complex (TSC1/2). Mutations in these components or in PTEN, a negative regulator of PI3-kinase, may result in their dysregulation. Abnormal functioning of various components of the signaling pathways contributes to the pathophysiology of numerous human cancers. Various preclinical models have confirmed the role of this pathway in tumor development [34].

The main known functions of mTOR include the following [35].

- mTOR functions as a sensor of mitogens, growth factors and energy and nutrient levels;
- Facilitating cell-cycle progression from G1-S phase in appropriate growth conditions;
- The PI3K/mTOR pathway itself is frequently dysregulated in many human cancers, and oncogenic transformation may sensitize tumor cells to mTOR inhibitors;
- PI3-kinase mutations have been reported in the primary tumor in 10-20% of human colorectal cancers [36, 37].

- The loss of PTEN protein, either through gene deletion or functional silencing (promoter hypermethylation), is reported in approximately 60% of primary human colorectal cancers [38].
- The mTOR pathway is involved in the production of pro-angiogenic factors (i.e., VEGF) and inhibition of endothelial cell growth and proliferation;
- Through inactivating eukaryotic initiation factor 4E binding proteins and activating the 40S ribosomal S6 kinases (i.e., p70S6K1), mTOR regulates protein translation, including the HIF-1 proteins. Inhibition of mTOR is expected to lead to decreased expression of HIF-1.

### 1.3.2 Non-clinical experience

Everolimus inhibits the proliferation of a range of human tumor cell lines *in vitro* including lines originating from lung, breast, prostate, colon, melanoma and glioblastoma. IC50s range from sub/low nM to  $\mu$ M. Everolimus also inhibits the proliferation of human umbilical vein endothelial cells (HUVECS) *in vitro*, with particular potency against VEGF-induced proliferation suggesting that Everolimus may also act as an anti-angiogenic agent. The anti-angiogenic activity of Everolimus was confirmed *in vivo*. Everolimus selectively inhibited VEGF-dependent angiogenic response at well tolerated doses. Mice with primary and metastatic tumors treated with Everolimus showed a significant reduction in blood vessel density when compared to controls.

The potential of Everolimus as an anti-cancer agent was shown in rodent models. Everolimus is orally bioavailable, residing longer in tumor tissue than in plasma in a subcutaneous mouse xenograft model, and demonstrating high tumor penetration in a rat pancreatic tumor model. The pharmacokinetic profile of Everolimus indicates sufficient tumor penetration, above that needed to inhibit the proliferation of endothelial cells and tumor cell lines deemed sensitive to Everolimus *in vitro*.

Everolimus administered orally daily was a potent inhibitor of tumor growth, at well tolerated doses, in 11 different mouse xenograft models (including pancreatic, colon, epidermoid, lung and melanoma) and two syngeneic models (rat pancreatic, mouse orthotopic melanoma). These models included tumor lines considered sensitive and “relatively resistant” *in vitro*. In general, Everolimus was better tolerated in mouse xenograft models than standard cytotoxic agents (i.e., doxorubicin and 5-fluorouracil), while possessing similar anti-tumor activity. Additionally, activity in a VEGF-impregnated subcutaneous implant model of angiogenesis and reduced vascularity (vessel density) of Everolimus-treated tumors (murine melanoma) provided evidence of *in vivo* effects of angiogenesis.

It is not clear which molecular determinants predict responsiveness of tumor cells to Everolimus. Molecular analysis has revealed that relative sensitivity to Everolimus *in vitro* correlates with the degree of phosphorylation (activation) of the AKT/PKB protein kinase and the S6 ribosomal protein; in some cases (i.e., glioblastoma) there is also a correlation with PTEN status.

*In vivo* studies investigating the anti-tumor activity of Everolimus in experimental animal tumor models showed that Everolimus monotherapy typically reduced tumor cell

growth rates rather than produced regressions. These effects occurred within the dose range of 2.5 mg to 10 mg/kg, orally once a day.

In preclinical models, the administration of Everolimus is associated with reduction of protein phosphorylation in target proteins downstream of mTOR, notably phosphorylated S6 (p-S6) and p-4E-BP1, and occasionally with an increase in phosphorylated AKT, a protein upstream of mTOR signaling pathway.

All significant adverse events observed in toxicology studies with Everolimus in mice, rats, monkeys and mini-pigs were consistent with its anticipated pharmacological action as an anti-proliferative and immunosuppressant and at least in part reversible after a 2 or 4-week recovery period with the exception of the changes in male reproductive organs, most notably testes.

In vitro genotoxicity studies covering relevant genotoxicity end-points showed no evidence of clastogenic or mutagenic activity.

In male fertility studies in rats, testicular morphology was affected at 0.5 mg/kg and above, and sperm motility, sperm head count and plasma testosterone levels were diminished at 5 mg/kg which corresponded to 0.7 times the estimated clinical exposure at 10 mg/day, and caused a decrease in male fertility. There was evidence of reversibility. Female fertility was not affected, but everolimus caused an increase of pre-implantation loss in female rats at doses > 0.1 mg/kg, suggesting it could also potentially impact fertility in females. Everolimus crossed the placenta and was toxic to the conceptus. In rats, everolimus caused embryo/fetotoxicity at systemic exposure below the planned therapeutic level comprising mortality and reduced fetal weight. The incidence of skeletal variations and malformations at 0.3 and 0.9 mg/kg (e.g. sternal cleft) was increased. In rabbits, embryo toxicity was evident by an increase in late resorptions. Effects of everolimus on the pre- and postnatal development of rats were limited to slightly affected body weight and survival in the F1-generation at  $\geq 0.1$  mg/kg, and did not indicate a specific toxic potential.

The potential reproductive risk for humans is unknown. However, due to the observed malformations in rats, everolimus should be considered potentially teratogenic. Everolimus should not be given to pregnant women unless the potential benefit outweighs the potential risk for the fetus. Women of childbearing potential should be advised to use highly effective contraception methods while they are receiving everolimus and up to 8 weeks after treatment has been stopped. It is not known whether everolimus is excreted in human milk. In animal studies, everolimus and/or its metabolites were readily transferred into the milk of lactating rats. Therefore women who are taking everolimus should not breastfeed.

Further details can be found in the Everolimus Investigator's Brochure.

## 2.0 RATIONALE

A phase II randomized study of neoadjuvant letrozole and everolimus vs. letrozole alone enrolled 270 postmenopausal patients with tumors larger than 2 cm, and showed improvements in clinical and radiographic responses [7]. However, this study did not select

patients by proliferation rate or recurrence score and thus likely included a broad mix of ER+ cancers. We propose a single arm phase II trial evaluating the combination of everolimus and an aromatase inhibitor in postmenopausal women with hormone receptor positive/HER2 negative breast cancers with low and intermediate risk ( $\leq 25$ ) Recurrence Scores by Oncotype Dx. The type of aromatase inhibitor administered during this trial will be at the physician's choice, since they all can be considered equivalent in activity based on the results of the ACOSOG Z1031 trial [1]. Our study eligibility will be limited to patients with 'low to moderately aggressive', hormone-responsive tumors, identified by recurrence score  $\leq 25$ , similar to the group of patients in whom the omission of adjuvant chemotherapy is being tested by the TAILORx and SWOG 1007 studies. Therefore, we propose to use pretreatment recurrence score to identify patients most likely to benefit from neoadjuvant endocrine therapy, and determine if the addition of the mTOR inhibitor everolimus enhances that response.

Our primary endpoint will be to evaluate response defined as a PEPI -0. Results from ACOSOG Z1031 demonstrated no difference in clinical response or surgical outcomes between luminal A vs luminal B tumors in postmenopausal patients treated with three different aromatase inhibitors, however, there were significantly higher responses defined by a Preoperative Endocrine Prognostic Index (PEPI) score of 0 in luminal A vs luminal B tumors (27.1% v 10.7 %; P=.0004) [1]. A PEPI score 0 was also highest in tumors with Ki67 levels  $<10\%$  at baseline. Kelly et al compared risk assignment by PAM 50 Breast cancer intrinsic classifier and Oncotype DX recurrence score in 151 hormone receptor positive stage I-II breast cancers [2]. The majority (83%) of low recurrence score cases were found to be luminal A subtype by PAM 50. Additionally, half of the intermediate recurrence scores were re-categorized as low risk luminal A subtypes by PAM 50. While there are no available reports of the incidence of PEPI-0 following neoadjuvant AI therapy in hormone receptor positive breast cancer patients with an Oncotype of  $\leq 25$ , Ellis et al did report a PEPI-0 of 27% in the Luminal A subset in ACOSOG Z1031. Therefore this will be used as our benchmark. Patients with clinical stage I –III (just like ACOSOG Z1031) hormone receptor tumors and RS  $<25$  will be eligible for the study.

An ongoing large randomized phase III clinical trial (SWOG 1007) is designed to evaluate the benefit from chemotherapy for ER positive breast cancer with 1-3 positive lymph nodes and an Oncotype Dx recurrence score of  $\leq 25$  (low-intermediate recurrence scores). It is likely that this tumor subset is more sensitive to a combination of an mTOR inhibitor and endocrine therapy. Our proposed neoadjuvant trial will provide rapid and complementary information to assess whether everolimus might improve the efficacy of endocrine therapy in breast cancers with low to intermediate recurrence scores.

### 3.0 STUDY OBJECTIVES

#### Primary objectives:

- The primary objective of the study is to determine the percent of postmenopausal patients with stage II-III hormone receptor positive/ HER2 negative breast cancer and an Oncotype Dx recurrence score  $\leq 25$  who achieve a PEPI score of 0 following neoadjuvant treatment with everolimus and an aromatase inhibitor

#### Secondary objectives:

- 1) To assess the tolerability and side effect profile of neoadjuvant aromatase inhibitor therapy and everolimus
- 2) To identify biologic markers predictive of clinical and pathologic response (pathologic complete response or PEPI 0) to neoadjuvant aromatase inhibitor therapy and everolimus in postmenopausal hormone receptor positive/HER2 negative breast cancer patients selected by Oncotype Dx Recurrence Score  $\leq 25$ , on tissue biopsies obtained at baseline and after completion of study treatment

### 4.0 TRIAL PATIENT POPULATION AND ELIGIBILITY

This trial which will enroll postmenopausal women with hormone receptor positive /HER2 negative breast cancers with low and intermediate risk ( $\leq 25$ ) Recurrence Scores by Oncotype Dx. The sample size for this study is 27 patients. Assuming that 10% of enrolled patients will be inevaluable , we plan to enroll up to 33 in total. Patients must have required baseline evaluations performed prior to the first dose of study drug and must meet all inclusion and exclusion criteria. The written informed consent must be obtained from the patient prior to enrollment. The following criteria apply to all patients enrolled onto the study unless otherwise specified.

#### 4.1 Inclusion criteria

1. Patients must have a histologically confirmed diagnosis of hormone receptor positive, HER2 negative invasive breast carcinoma.
2. Tumors must be estrogen and/or progesterone receptor positive according to ASCO/CAP 2010 guidelines as either ER or PR  $\geq 1\%$  positive nuclear staining by immunohistochemistry. Estrogen and/or progesterone receptor results by Oncotype Dx will not be accepted.
3. Tumors must be HER2 negative as defined according to ASCO/CAP 2013, as HER2 0 – 1+ by IHC or non-amplified FISH or CISH. If HER2 IHC is 2+, FISH/CISH must be performed and must not be positive (must be a ratio of  $< 2$ ), but otherwise FISH/CISH is not required if IHC is 0 or 1+ by institutional standards.
4. Patients must not have had prior ipsilateral breast-conserving surgery or total mastectomy and be eligible for neoadjuvant treatment.
5. Clinical Stage II-IIIC (T2-4 N0-3 M0) by mammogram, ultrasound or MRI

6. Baseline Oncotype Dx recurrence score  $\leq 25$ .
7. Staging studies with a CT scan of the chest and abdomen and bone scan, or a PET/CT is required for clinical stage III, and are considered optional for stage II breast cancers.
8. Patients with multifocal, multicentric and synchronous bilateral breast cancers are allowed:
  - Multifocal disease is defined as more than one invasive cancer  $< 2$  cm from the largest lesion within the same breast quadrant.
  - Multicentric disease is defined as more than one invasive cancer  $\geq 2$  cm from the largest lesion within the same breast quadrant or more than one lesion in different quadrants.
  - Synchronous bilateral disease is defined as invasive breast cancer in both breasts, diagnosed within 30 days of each other. In patients with multicentric or bilateral invasive breast cancers, all sampled lesions must be hormone receptor-positive.. Any lesion measuring  $\geq 1$  cm must have an Oncotype Dx and the score must be  $\leq 25$ . Lesions less than 1 cm in size are not required to have an Oncotype Dx. One lesion (typically the largest) should be designated as the target lesion for which clinical and radiographic response to the neoadjuvant therapy will be judged.
  - Patients with a hormone receptor-positive, HER2-negative invasive cancer that meets study criteria may have ductal carcinoma in situ in another quadrant of the same breast or in the contralateral breast even if the DCIS is hormone receptor-negative.
9. Patients must have adequate bone marrow function, as defined by peripheral granulocyte count of  $\geq 1,500/\text{mL}$ , hemoglobin  $\geq 9 \text{ g/dL}$  and a platelet count  $\geq 100,000/\text{mL}$  within 28 days prior to registration.
10. Patients must have adequate hepatic function obtained within 28 days prior to registration and documented by all of the following:
  - Bilirubin  $\leq 1.5 \text{ mg/dL}$  (or  $\leq 3.0 \text{ mg/dL}$  if due to Gilbert's Syndrome)
  - ALT and AST  $\leq 1.5 \times$  Institutional Upper Limit of Normal (IULN)
  - Alkaline phosphatase  $\leq 1.5 \times$  IULN
11. Patients must have adequate renal function with serum creatinine level  $\leq$  IULN within 28 days prior to registration.
12. Patients must have a fasting cholesterol  $\leq 300 \text{ mg/dL}$  OR  $\leq 7.75 \text{ mmol/L}$  and triglycerides  $\leq 2.5 \times$  IULN obtained within 28 days prior to registration. Patients may be on lipid lowering agents to reach these values.
13. Patients must have a ECOG performance status of 0-2.
14. Patients must be able to take oral medications.

15. Postmenopausal women (women are considered post-menopausal and not of child-bearing potential if they are > 18 years of age and have had 12 months of natural (spontaneous) amenorrhea with an appropriate clinical profile (e.g. age appropriate, history of vasomotor symptoms or biochemically postmenopausal by estradiol and FSH levels)) prior to enrollment or have had surgical bilateral oophorectomy (with or without hysterectomy) prior to registration. Medical ovarian suppression with LHRH agonists to render a patient postmenopausal will not be acceptable.
16. Patients or their legally authorized representative must be informed of the investigational nature of this study and must sign and give written informed consent prior to any screening procedures in accordance with institutional and federal guidelines.

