### **14.3 Sample Size calculation**

This is a single arm phase II study to evaluate neoadjuvant endocrine therapy with everolimus in postmenopausal women with ER+/HER2 – breast cancers with low and intermediate risk ( $\leq 25$ ) Recurrence Scores. The primary endpoint will be response defined as a PEPI-0 rate. A treatment with minimal activity would be expected to have PEPI-0 rate of 25%. Alternatively, a treatment will be considered worthy of further study if its true PEPI-0 rate is 45% or better.

Simon's optimal two-stage design is employed for this single-arm phase II trial and a total of 27 eligible patients will be enrolled. First, 15 eligible patients will be enrolled in the study. If 5 or more of 15 eligible patients achieve a PEPI score of 0, we will enroll another 12 patients into the study. If 10 or more of the 27 eligible patients achieve a PEPI score of 0, we will conclude that the regimen warrants further study. This design has a power of 80% and a one-sided significance level of 0.1. The probability of stopping early if the treatment is ineffective (true PEPI-0 rate of  $\leq 25\%$ ) is 69%. Assuming that 10-20% of enrolled patients will be invaluable, we plan to enroll up to 33 in total.

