## APPENDIX B

### The preoperative endocrine prognostic index

Pathology, biomarker status	RFS		BCSS	
	HR	Points	HR	Points
Pathological tumor size				
T1/2	—	0	—	0
T3/4	2.8	3	4.4	3
Node status				
Negative	—	0	—	0
Positive	3.2	3	3.9	3
Ki67 level				
0%–2.7% (0–1†)	—	0	—	0
>2.7%–7.3% (1–2†)	1.3	1	1.4	1
>7.3%–19.7% (2–3†)	1.7	1	2.0	2
>19.7%–53.1% (3–4†)	2.2	2	2.7	3
>53.1% (>4†)	2.9	3	3.8	3
ER status, Allred score				
0–2	2.8	3	7.0	3
3–8	—	0	—	0

\*To obtain the preoperative endocrine prognostic index (PEPI) score, risk points for relapse-free survival (RFS) and breast cancer-specific survival (BCSS) were assigned depending on the hazard ratio (HR) given in Table 3. The points scale was adapted from the cardiovascular literature on predicting outcomes for myocardial infarction (11). The total PEPI score assigned to each patient is the sum of the risk points derived from the pT stage, pN stage, Ki67 level, and estrogen receptor (ER) status of the surgical specimen. An HR in the range of 1–2 receives one risk point; a HR in the 2–2.5 range, two risk points; a HR greater than 2.5, three risk points. The total risk point score for each patient is the sum of all the risk points accumulated from the four factors in the model. For example, a patient with a T1N0 tumor, a Ki67 staining percentage of 1 and an ER Allred score of 6 will have no risk points assigned. In contrast, a patient with a T3N1 tumor, a Ki67 staining percentage of 25, and an ER Allred score of 2 will have a total relapse score of  $3 + 3 + 2 + 3 = 11$ .

†The natural logarithm interval corresponding to the percent Ki67 values on the original percentage scale

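### Tumours that are ER-negative but PR-positive are eligible, yet one still at ER Allred 0-2 at surgery cannot score PEPI-0, and the plan is inconsistent on whether its 25%/45% rates include such patients

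*Combined protocol and SAP*

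**What the plan says.** **Eligibility.** Section 4.1, item 2 (same wording in the synopsis): "Tumors must be estrogen and/or progesterone receptor positive according to ASCO/CAP 2010 guidelines". The item is met by either receptor at 1% staining or more. No exclusion in section 4.2 removes a tumour that is positive for PR alone.

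**Endpoint.** Section 14.1 makes PEPI score 0, as defined in Appendix B, the primary endpoint. In the Appendix B table, under "ER status, Allred score", a score of 0-2 carries 3 points and a score of 3-8 carries none. The total is the sum over tumour size, nodes, Ki67 and ER. ER is taken from the surgical specimen, and section 9.6 has it re-measured there for this purpose.

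**Sample size.** Section 14.3 describes the population as "postmenopausal women with ER+/HER2"-negative. It sets the null rate with "A treatment with minimal activity would be expected to have PEPI-0 rate of 25" per cent, and the alternative with "a treatment will be considered worthy of further study if its true PEPI-0 rate is 45% or better". The rules are "If 5 or more of 15 eligible patients achieve a PEPI score of 0, we will enroll another 12 patients into the study" and "If 10 or more of the 27 eligible patients achieve a PEPI score of 0, we will conclude that the regimen warrants further study". The stated power is 80% at a one-sided level of 0.1.

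**Other descriptions of the population.** The synopsis paragraph on statistical methodology gives the same rates, design and sample size but calls the population hormone receptor positive. The primary objective in section 3.0 does the same.

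**The concern.** No component of the PEPI score is negative, so three points from ER alone rule out a total of 0. A patient who enters ER-negative and is still at Allred 0-2 at surgery is evaluable and is counted as a failure, however well the tumour responds in size, nodes and Ki67. The 10-20% allowance in section 14.3 does not help, because it covers inevaluable patients and she is evaluable.

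With 27 patients and a cut-off of 10, one built-in failure matters. At stake is the chance of missing an active regimen: stopping after 15 patients or falling short at 27 because of who was enrolled. Whether the stated power already allows for this depends on which population the 45% describes, and the plan's descriptions of that population differ.

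**Working it through.** **Inputs (section 14.3).** Null rate 0.25 and target rate 0.45. Stage 1 has 15 patients and continues with 5 or more PEPI-0. Stage 2 adds 12, and success is 10 or more of 27.

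**Step 1: reproduce the stated design.**

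P(success) = Σ over x from 5 to 15 of P[Bin(15, p) = x] × P[Bin(12, p) ≥ 10 − x]

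- p = 0.45: 0.801 (stated 80%).
- p = 0.25: 0.097 (stated level 0.1).
- Early stopping at p = 0.25, P[Bin(15, 0.25) ≤ 4] = 0.686 (stated 69%).

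The design is computed correctly for a true rate of 45%.

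**Step 2: add built-in failures, with 45% holding in the other patients.** If k1 of them fall in stage 1 and k2 in stage 2, the formula becomes

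Σ over x from 5 to 15 − k1 of P[Bin(15 − k1, p) = x] × P[Bin(12 − k2, p) ≥ 10 − x]

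For one such patient, power is 0.743 if she is in stage 1 and 0.772 if she is in stage 2. With random placement:

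(15/27) × 0.743 + (12/27) × 0.772 = 0.756

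Averaging over random placement for larger numbers, and applying the same formula with p = 0.25 for type I error if the null rate is diluted in the same way:

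| Built-in failures among 27 | Power (45% in the others) | Type I error (25% in the others) |
|---|---|---|
| 0 | 80.1% | 9.7% |
| 1 | 75.6% | 7.8% |
| 2 | 70.4% | 6.1% |
| 3 | 64.5% | 4.6% |

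One such patient in stage 1 also raises the chance of stopping early at a 45% rate from P[Bin(15, 0.45) ≤ 4] = 12.0% to P[Bin(14, 0.45) ≤ 4] = 16.7%. Averaged over where she falls, it is (15/27) × 16.7% + (12/27) × 12.0% = 14.6%.

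**Step 3: the other reading, with 45% as the rate in everyone enrolled.** With one built-in failure, the other 26 must respond at 0.45 × 27/26 = 0.467. The formula in step 2 then gives power of 80.5%, so nothing is lost.

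**Step 4: how many such patients?** The documents give no share. Entry also requires a Recurrence Score of 25 or less. The counts of 1 to 3 are assumptions that show the range, and zero is possible.

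**The case against.** The strongest reply is that the rates were never set for ER-positive patients alone. Only section 14.3 says ER+. The synopsis paragraph with the same rates and design says hormone receptor positive, as do the title, the objective, the population section and the design section. The rationale in section 2.0 also frames the missing benchmark in terms of hormone receptor positive patients before borrowing 27% from a Luminal A subset. On that reading, ER+ is loose wording, 45% is the rate in everyone enrolled, and power is about 80%. This stands: a reader might infer that the stated 80% is wrong or is lost as soon as one such patient enters, and the documents do not support that.

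Two further limits stand. A reader might infer that every patient who enters ER-negative is bound to fail. Eligibility, however, uses percent staining on the baseline biopsy, while PEPI uses an Allred score at surgery, and nothing in the plan maps one to the other. Failure is the expected result, but it is certain only for a tumour at Allred 0-2 at surgery. Nor is there a false-positive risk: if the null rate is diluted too, type I error falls.

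It can also be argued that enrolling and counting all hormone receptor positive patients is what the objective asks for, and that correcting one phrase in section 14.3 would be enough. That would remove the inconsistency. It would not remove patients who are expected to fail for a reason unrelated to the treatment.

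**Conclusion.** The point holds in a conditional form. Eligibility admits tumours positive for PR alone. The endpoint makes any tumour still at ER Allred 0-2 at surgery a failure whatever the treatment does. The documents do not agree on whether the 25% and 45% rates describe ER-positive or all hormone receptor positive patients.

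If 45% applies to ER-positive patients, each of the first two such patients costs about 5 points of power (80.1% to 75.6% to 70.4%). This assumes that they stay at Allred 0-2 and fall at random among the 27. If 45% applies to everyone enrolled, the cost is nil. The number of such patients is unknown and may be zero. The design is not invalid and its calculation is right; what is offered is a cheap improvement.

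**What to change.** Before any outcome data are seen, choose one of these:

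1. Change inclusion criterion 2 (section 4.1 and the synopsis) to require ER of at least 1%.
2. Keep patients positive for PR alone eligible, but state in section 14.3 that those who are ER-negative on the baseline biopsy are left out of the 15 and the 27 that decide, and are reported separately. Use baseline ER only. ER at surgery is part of the outcome and must not be used to remove patients.

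Under either choice, use the same population wording in the objective, the synopsis and section 14.3, and say that the 25% and 45% rates refer to it.

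**Cost.** One eligibility or analysis-set sentence plus the matching wording. Baseline ER is already collected. A few patients positive for PR alone are lost or not counted, and the conclusion then applies to ER-positive patients.
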